1.2. Study Design

1.2.1. Design Configuration and Subject Population

This is a randomized, multicenter, open-label (OL), 2-part study in adult male and female subjects with HIV who are coinfected with chronic genotype 1 HCV infection. Eligible subjects had maintained HIV-1 RNA < 50 copies/mL for at least 6 months on a stable ARV therapy met one of the following criteria:

- 1) No cirrhosis and no prior HCV treatment (treatment-naive);
- 2) No cirrhosis and have receive HCV treatment only with interferon (IFN) ± ribavirin (RBV) or IFN + RBV + an HCV protease inhibitor (PI) (ie, treatment experienced)
- 3) Compensated cirrhosis and no prior HCV treatment (treatment naive)

1.2.2. Randomization and Treatment Groups

Part 1: Approximately 120 subjects will be randomized 1:1 to switch from stable ARV therapy to 1 of the following treatments:

- **Treatment Group 1:** Switch from 2 nucleoside/nucleotide reverse transcriptase inhibitor (NRTI) plus a third ARV agent to E/C/F/TAF fixed dose combination (FDC) (n = 60)
- Treatment Group 2: Switch from 2 NRTI plus a third ARV agent to F/R/TAF FDC (n = 60)

Randomization will be stratified by race (black vs non-black).

Part 2: After 8 weeks on the randomized F/TAF-based regimens, subjects maintaining HIV-1 RNA < 50 copies/mL and tolerating E/C/F/TAF or F/R/TAF through Part 1 will continue the F/TAF-based HIV therapy to which they were randomized and initiate LDV/SOF HCV treatment.

• LDV/SOF FDC tablet once daily for 12 weeks.

1.2.3. Key Eligibility Criteria

- Chronic genotype 1, HCV infected, male and nonpregnant/non-lactating female subjects. Subjects without cirrhosis who were HCV treatment naive or treatment experienced with IFN ± RBV ± HCV PI. Subjects with compensated cirrhosis must have been HCV treatment naive. Subjects with no prior treatment with an HCV nonstructural protein NS5A, and NS5B, or any HCV direct-acting antiviral (DAA), except boceprevir, telaprevir, or simeprevir in combination with IFN and RBV.
- Currently taking an ARV regimen (2 NRTI + a third agent) without change for 6 months prior to screening. Documented plasma HIV-1 RNA < 50 copies/mL (or undetectable HIV-1 RNA according to the local assay if the limit of detection is ≥ 50 copies/mL) for ≥ 6 months preceding the screening. After reaching HIV-1 RNA < 50 copies/mL, single values ("blips") of HIV-1 RNA ≥ 50 copies/mL followed by resuppression will be allowed. For subjects with 3 or more prior ARV regimens, a regimen history should be provided for approval by the sponsor.
- Plasma HIV-1 RNA < 50 copies/mL at the screening visit.
- With no documented history of resistance to any of the HIV study agents, including but not limited to the reverse transcriptase resistance mutations K65R, K70E, K101E/P, E138A/G/K/R/Q, V179L, Y181C/I/V, M184V/I, Y188L, H221Y, F227C, M230I/L, the combination of K103N+L100I, or 3 or more thymidine analog associated mutations (TAMs) that include M41L or L210W (TAMs are M41L, D67N, K70R, L210W, T215Y/F, K219Q/E/N/R). If a historical genotype prior to first ARV is not available or a subject had 3 or more prior ARV regimens, the subject will have proviral genotype analysis for archived resistance prior to Day 1.

1.2.4. Study Periods

Part 1: Subjects will be randomized to receive E/C/F/TAF or F/R/TAF for 8 weeks.

Part 2: Subjects will receive 12 weeks of LDV/SOF and continue their randomized F/TAF-based regimen for 12 weeks after completion of LDV/SOF (total approximately 24 weeks in Part 2).

After a subject has completed/terminated their participation in the study, long-term care for the subject will remain the responsibility of their primary treating physician.

1.2.5. Schedule of Assessments

After obtaining informed consent, screening assessments will be completed within 42 days prior to the Day 1 visit, including physical examination, height, weight, vital signs, medical history, 12-lead electrocardiogram (ECG), screening procedure-related adverse events (AEs), concomitant medications (CMs), clinical laboratory tests (including hematology, coagulation, and chemistry, and), urinalysis, plasma concentrations of HIV-1 RNA and HCV RNA, serology (HIV, HCV, hepatitis B virus [HBV]), historical HIV resistance (if not available; HIV DNA archive genotype), HCV genotyping, IL28B genotyping, cirrhosis determination, serum β -hCG (females of child bearing potential only).

On treatment assessment will occure as follows:

- **Part 1:** Switch to F/TAF-based ARV regimen:
 - Day 1 and Weeks 4, 6 (HIV-1 RNA only), and 8
- Part 2: LDV/SOF treatment and follow-up
 - At first dose of LDV/SOF at Week 8, and at Weeks 12, 16, and 20 (ie, 4, 8, and 12 weeks after start of LDV/SOF) and follow up at 4 and 12 weeks post LDV/SOF treatment.

On treatment and post HCV treatment assessments will include HIV-1 RNA and HCV RNA plasma concentrations, CD4 cell count, adherence to study drug dosing (including pill count), physical examination, weight, vital signs, clinical laboratory tests, urine pregnancy tests (females of child bearing potential only), monitoring of AEs and CMs, and patient-reported quality-of-life (QoL) assessments.

Fasting lipid profile measurements and fasting glucose will be performed at Day 1, Weeks 8 and 20, and at Post HCV Treatment Week 12. Lipids will include total cholesterol (TC), high density lipoproteins (HDL), low density lipoproteins (LDL), non-HDL cholesterol, triglycerides (TGs) and cholesterol ratios.

Post HIV treatment assessments (30 days after the last dose of HIV study drug) will include HCV RNA, HIV RNA, CD4 count, physical examination (including vital signs and weight), 12-lead ECG, clinical laboratory tests (including hematology, chemistry, and urinalysis, urine pregnancy tests (females of childbearing potential only), and AEs and CMs.

Plasma samples for HCV RNA and HIV-1 RNA will be collected at Day 1 and every visit thereafter (no HCV RNA at Weeks 4 and 6).

Calculated creatinine clearance, hematology, serum chemistry, and urinalysis tests will be performed at all study visits and early study drug discontinuation (ESDD) visits as applicable.

Health Related Quality of Life (HRQoL) surveys will be conducted at Day 1, Weeks 8, 20, and Post HCV Treatment Week 12 and ESDD visits as applicable.

PPD

Blood samples for population pharmacokinetic (PK) evaluation will be collected at Weeks 4, 8, 12, 16, and 20.

1.2.6. Site and Stratum Enrollment Limits

Approximately 50 centers in North America will participate. There is no enrollment limit for individual sites.

1.3. Sample Size and Power

A sample size of 120 subjects will provide at least 85% power to detect an improvement of at least 8% in overall SVR12 rate from the performance goal of 88%, by using a 2-sided exact 1-sample binomial test at a significance level of 0.05.

2. TYPE OF PLANNED ANALYSIS

2.1. Post HCV Treatment Week 4 Analysis

A post HCV treatment Week 4 analysis will be conducted for administrative purposes after all subjects have completed the post HCV treatment Week 4 visit or prematurely discontinue from the study. All safety and efficacy data through the post HCV treatment Week 4 visit will be included. There will be no changes to the study design, study conduct, or the sample size as a result of this administrative analysis.

2.2. Final Analysis (SVR12 Analysis)

The analysis for the primary endopoint SVR12 will occur after all subjects have either completed the study, including the 30-Day Follow-Up Visit, or prematurely discontinued from the study, outstanding data queries have been resolved, and the database has been cleaned and finalized.

3. GENERAL CONSIDERATIONS FOR DATA ANALYSES

Analysis results will be presented using descriptive statistics. For categorical variables, the number and percentage of subjects in each category will be presented; for continuous variables, the number of subjects (n), mean, standard deviate (SD) or standard error (SE), median, first quartile (Q1), third quartile (Q3), minimum, and maximum will be presented.

By-subject listing will be presented for all subjects in the All Randomized analysis set unless otherwise specified, and sorted by subject ID number, visit date, and time (if applicable). Data collected on log forms, such as AEs, will be presented in chronological order within a subject. The treatment group to which subjects were randomized will be used in the listings.

In general, age (in years) on the earliest date of the first dose of study drug, including E/C/F/TAF, F/R/TAF, and LDV/SOF, will be used for presentation in listings. For randomized but never dosed subjects, age on the date of randomization will be used. For screen failures, age on the date of the informed consent was signed will be used. If only birth year is collected on the eCRF, "01 January" will be used for the unknown birth day and month for the purpose of age calculation, similarly, if only birth year and month are collected on the eCRF, "01" will be used for the unknown birth day for the purpose of age calculation.

In general, permanent discontinuation of study drug refers to premature discontinuation of study drug or planned completion of study drug.

3.1. Analysis Sets

Analysis sets define the subjects to be included in an analysis. Analysis sets and their definitions are provided in this section. The analysis set will be included as a subtitle of each table, figure, and listing. A summary of the number and percentage of subjects in each analysis set will be provided by treatment group and in total.

3.1.1. All Randomized Analysis Set

The **All Randomized Analysis Set** will include all subjects who are randomized into the study. This is the primary analysis set for by-subject listings except for HCV efficacy endpoint listings, which are based on HCV Full Analysis Set defined in Section 3.1.2.2.

3.1.2. Efficacy Analysis Sets

For this HIV/HCV-coinfection study, the data will be analyzed to assess the treatment efficacy to both HIV and HCV. Therefore, efficacy analysis sets will be defined separately for the HIV drugs, E/C/F/TAF and F/R/TAF, and the HCV drug, LDV/SOF.

HIV Full Analysis Set

The HIV Full Analysis Set (HIV FAS) will include all subjects who (1) are randomized into the study and (2) have received at least 1 dose of HIV study drug, E/C/F/TAF or F/R/TAF. Subjects will be grouped according to the treatment to which they were assigned at randomization. For the HIV FAS, all efficacy data, including data collected after the last dose of HIV study drug, will be included, unless specified otherwise. This is the primary analysis set for the efficacy analyses of HIV study drug.

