3.4. Duration of Treatment

The HIV treatment duration is from the Day 1 visit until the last study visit at the Post-HCV Treatment Week 12. The HCV treatment duration is 12 weeks. Screening assessments will be completed within 42 days of the Day 1 visit.

All subjects will complete the following study visits: Screening, Day 1, Weeks 4, 6 (laboratory visit only), 8 (start of HCV treatment), 12, 16, and 20 (end of HCV treatment), and post-HCV treatment visits 4 and 12 weeks after the last LDV/SOF dose.

Subjects who complete the study through the last study visit at the Post-HCV Treatment Week 12 visit will be required to return to the clinic 30 days after the completion of the study treatment for a 30-Day Follow-Up visit.

- a Following the Day 1 visit, subjects will return for study visits at Weeks 4, 6 (laboratory visit only), 8, 12, 16, 20, and Post-HCV Treatment 4 and 12 weeks after the last LDV/SOF dose.
- b Part 1: subjects are randomized to either E/C/F/TAF FDC or F/R/TAF FDC on Day 1 and maintain HIV treatment to the Week 8 visit.
- c Part 2: At Week 8, once HIV-1 RNA suppression (< 50 copies/mL) is confirmed (based on the Week 6 HIV-1 RNA value), subjects will start on LDV/SOF FDC for 12 weeks (until Week 20) while maintaining their HIV treatment. At Week 20, LDV/SOF FDC will be discontinued while continuing HIV treatment. Subjects will continue in the study for another 12 weeks to determine SVR4 (4 weeks post-HCV treatment) and SVR12 (12 weeks post-HCV treatment).

- d Subjects who complete the study through the Post-HCV Treatment Week 12 visit will be required to return to the clinic 30 days after the completion of the study treatment for a 30-Day Follow-Up Visit.
- e At the Day 1 visit, subjects will switch to either E/C/F/TAF FDC or F/R/TAF FDC and continue on HIV treatment until the last study visit at the Post-HCV Treatment Week 12 visit.

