- Upon confirmation of HIV-1 RNA ≥ 50 copies/mL, potential causes of virologic failure should be documented. Assessment should include:

- Adherence

- Concomitant medication
- Comorbidities (eg, active substance abuse, depression, other intercurrent illnesses)
- All subjects with confirmed virologic failure should be discussed with the Medical Monitor.
- If virologic rebound is confirmed at the scheduled or unscheduled visit and the HIV-1 RNA value is ≥ 400 copies/mL, the blood samples from that visit will be used for HIV-1 genotype/phenotype testing.
- If genotypic/phenotypic resistance to study drug is documented, HIV study drugs (E/C/F/TAF or F/R/TAF) should be discontinued.
- If the HIV study drugs (E/C/F/TAF or F/R/TAF) are discontinued, a new HIV regimen should be constructed, after discussion with the Medical Monitor. The new HIV regimen should be designed to allow continued dosing of LDV/SOF. LDV/SOF should be continued unless an HIV regimen cannot be constructed that would allow coadministration with the new HIV regimen.

If no resistance is detected from genotype/phenotype testing, the subject may remain on HIV study drugs and an HIV-1 RNA should be repeated (2 to 4 weeks after date of test with viral load \geq 50 copies/mL). Investigators should carefully evaluate the benefits and risks of remaining on HIV study drug for each individual subject and document this assessment in the source documents. Investigators who opt to discontinue HIV study drugs for an individual subject must discuss with the Medical Monitor prior to study drug discontinuation.

Please refer to Figure 6-1 for the management of subjects who meet the criteria for virologic rebound.

Figure 6-1. HIV Virologic Rebound Schema

- a If virologic rebound is not confirmed, the subject will remain on their current HIV regimen.
- b If virologic rebound is confirmed, and the HIV-1 RNA is \geq 400 copies/mL, the HIV-1 genotype and phenotype (reverse transcriptase, integrase, and protease) will be analyzed.
- c Based on the results of the genotype/phenotype assays, the subject will remain on HIV study drugs or study drugs will be discontinued. If genotyping/phenotyping fails, a new ARV regimen may be configured at the discretion of the Investigator.
- d If no resistance detected, HIV-1 RNA will be repeated (2 to 4 weeks later). Investigator reviews HIV study drug continuation/discontinuation options and discuss with Medical Monitor prior to study drug discontinuation.

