 - For other numeric observations (eg, except HIV-1 RNA, HCV RNA, CD4+ cell count, and CD4%), the record(s) collected on the day closest to the nominal day for that visit will be selected. If there are 2 days equidistant from the nominal day, the later day will be selected.
 - For any numeric observations except HIV-1 RNA, If there is more than 1 record on the selected day, the average (arithmetic mean) will be taken.
- For baseline and postbaseline HIV-1 RNA, the latest (considering both date and time) record(s) in the window will be selected. If both "HIV RNA Taqman 2.0" and "HIV RNA Repeat" (ie, the HIV-1 RNA result obtained from an additional aliquot of the original sample) are available with the same collection time, the results from the "HIV RNA Repeat" will be selected for analysis purposes; otherwise, if there are multiple "HIV RNA Taqman 2.0" records with the same collection time, the geometric mean will be taken for analysis purposes.

If multiple valid nonmissing categorical observations exist in an analysis window, records will be selected as follows:

- For baselines, the last available record on or prior to the first dose dates of study drugs will be selected. If there are multiple records with the same time or no time recorded on the same day, the value with the lowest severity will be selected (eg, normal will be selected over abnormal).
- For postbaseline visits, follow the same rules described above for postbaseline numeric observations, except that if there are multiple records with the same time or no time recorded on the same day, the value with the highest severity will be selected (eg, abnormal will be selected over normal).

PROs do not apply to above since no analysis window is assigned. For each nominal visit, if multiple observations exist, records will be set to missing.

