6. EFFICACY ANALYSES

The efficacy analyses include analyses of both HCV study drug (LDV/SOF) efficacy and HIV study drug (E/C/F/TAF and F/R/TAF) efficacy. The analysis of HCV efficacy endpoints will use HCV FAS, and the analysis of HIV efficacy endpoints will use HIV FAS.

In efficacy analysis, HCV efficacy data (HCV RNA) collected from the first dose date of LDV/SOF up to the last dose date of LDV/SOF + 3 days are considered **on-HCV-treatment** data; HIV efficacy data (HIV-1 RNA, CD4+ cell count, and CD4%) collected from the first dose date of HIV study drug up to the last dose date of HIV study drug + 1 day are considered **on-HIV-treatment** data.

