The proportion of subjects with HIV-1 RNA < 50 copies/mL will also be analyzed using the M = F and M = E for imputing missing HIV-1 RNA values, where the proportions will be expressed as percentages in all tables, listings, and figures.

For both M = F and M = E analyses, the number and percentage of subjects with HIV-1 RNA in the following categories will be summarized:

- < 50 copies/mL
- < 20 copies/mL
 - < 20 Not Detectable
 - < 20 Detectable
- 20 to < 50 copies/mL
 - $-- \ge 50 \text{ copies/mL}$
 - Missing (only applicable for M = F analysis)

The proportion of subjects with HIV-1 RNA < 50 copies/mL as defined by the 2 different missing data imputation methods will be summarized by treatment group and overall. The differences in proportions of subjects with HIV-1 RNA < 50 copies/mL using M = E and M = F imputation methods between the 2 treatment groups and the corresponding two-sided exact 95% CIs will be calculated based on an unconditional exact methods using 2 inverted 1-sided tests. In addition, the 95% CI of the proportion of subjects with HIV-1 RNA < 50 copies/mL within each treatment at each visit will be provided using the Clopper-Pearson Exact method.

For both M = F and M = E analysis, results will be summarized by treatment group for all visits.

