6.3.2.7. Analysis of CD4+ Cell Count and CD4 %

Both CD4 cell count and CD4 % will be summarized using observed, on-HIV-treatment data (ie, data collected up to 1 day after permanent discontinuation of HIV study drug or all available data for subjects who are still on HIV study drug) for subjects in the HIV FAS.

The change from baseline in CD4+ cell count will be summarized by visit for each treatment group and over all using descriptive statistics. The differences in changes from baseline 24 weeks after start of HIV study drug in CD4+ cell count between the 2 treatment groups and the associated 95% CI will be constructed using ANOVA models, including treatment group and race as fixed effects.

In addition, the change from baseline in CD4+ cell counts with missing values imputed using the last observation carried forward (LOCF) method will be summarized at each visit based on the FAS. The algorithm for LOCF as follows:

- If a value is missing in an analysis visit window, the missing value will be replaced with the last on-HIV-treatment value (ie, data collected up to 1 day after the last dose date of HIV study drug) observed before the analysis visit window that has the missing value.
- Baseline values will be carried forward to impute the postbaseline value at a specific visit, if there is no nonmissing postbaseline observation collected prior to that visit.

CD4% will be analyzed the same as CD4+ cell count, except that the by-visit summary using LOCF method is not planned for CD4%.

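### In the tertiary M = F and M = E analyses of HIV-1 RNA < 50 copies/mL, the Week 32 value comes from the 30-Day Follow-Up, after study drug has ended, and not from the on-drug Post-HCV Treatment Week 12 visit

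*SAP*

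**What the plan says.** SAP 6 states that "the analysis of HIV efficacy endpoints will use HIV FAS", and SAP 3.1.2 sets the data rule for that set: "For the HIV FAS, all efficacy data, including data collected after the last dose of HIV study drug, will be included, unless specified otherwise". SAP 6 also defines a narrower class. HIV data "up to the last dose date of HIV study drug + 1 day are considered" on-HIV-treatment. That definition limits an analysis only where the analysis invokes it.

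Two analyses do. The Week 24 snapshot (SAP 6.2.2.2, and the 20-copy version in 6.3.2.5 by reference) uses on-HIV-treatment data in a closed window, Days 155 to 196. For CD4, SAP 6.3.2.7 says: "Both CD4 cell count and CD4 % will be summarized using observed, on-HIV-treatment data".

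The M = F and M = E analyses do not. SAP 6.3.2.6 says that the proportion below 50 copies/mL "will also be analyzed using the M = F and M = E for imputing missing HIV-1 RNA values", at all visits, with between-arm differences and exact confidence intervals. Neither it, nor SAP 3.6.1.3, nor SAP Appendix 4 item 11 limits the data to time on study drug.

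On record selection, SAP 3.8.3 says: "For baseline and postbaseline HIV-1 RNA, the latest (considering both date and time) record(s) in the window will be selected". SAP 3.8.2.1 explains that Weeks 24 and 32 are names for the Post-HCV Treatment Week 4 and Week 12 visits.

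Under Protocol 3.4, subjects "continue on HIV treatment until the last study visit at the Post-HCV Treatment Week 12 visit". Protocol 6.5.2 then requires completers to attend a 30-Day Follow-Up at which plasma HIV-1 RNA is drawn. For subjects whose HIV study drug is stopped in Part 2, Protocol 6.9.1 says "a new HIV regimen should be constructed, after discussion with the Medical Monitor", and Protocol 6.5.1 keeps them in the study with further visits.

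**The concern.** Week 32 is the end of randomised HIV treatment, and the M = F and M = E tables are the only planned HIV-1 RNA responder analysis at that visit, because the snapshot closes at Day 196. A reader will take the Week 32 row as suppression on the assigned regimen at the end of treatment. If the selection rules put a post-treatment sample in that row, the arm rates and the between-arm interval describe something else. A subject suppressed at the last on-drug visit who lapses once study supply ends would count as a failure of the regimen. A subject not suppressed on drug who is suppressed a month later would count as its success.

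A smaller issue of the same kind affects earlier visits. A Part 2 subject who stops HIV study drug, changes regimen and is then suppressed counts as a success of the randomised arm at later visits, because an off-drug value is not a missing value under M = F.

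**Working it through.** The plan states no figure on this point, so the check maps the visit schedule onto the windows and applies the selection rules.

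**Inputs**
- LDV/SOF starts at Week 8 (Day 56) and lasts 12 weeks; follow-up is a further 12 weeks (Protocol 3.4).
- Post-HCV Treatment Week 12 visit window: ± 4 days (Protocol 6.4.2). HIV study drug ends at this visit and none is dispensed there (Protocol Appendix 2, footnote u).
- 30-Day Follow-Up: 30 days later, ± 6 days (Protocol 6.5.2).
- Week 32 HIV-1 RNA window: Day 197 onward (SAP Table 3-1).
- On-HIV-treatment limit: last dose + 1 day (SAP 6).

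**Step 1: which samples fall in the Week 32 window**
- Post-HCV Treatment Week 12: 56 + 84 + 84 = Day 224; with ± 4 days, Day 220 to 228.
- 30-Day Follow-Up: 224 + 30 = Day 254. Earliest 220 + 24 = Day 244; latest 228 + 36 = Day 264.
- Both are later than Day 197, so both are in the window.

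**Step 2: which sample is selected**
- The follow-up comes 24 to 36 days after the on-drug sample, so the latest-record rule always selects it.
- It is 24 − 1 = 23 to 36 − 1 = 35 days past the on-HIV-treatment limit.
- This holds for every completer who attends the follow-up. SAP 2.2 places the final analysis after that visit, so the data will be available.

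**Step 3: look for a rule that removes the follow-up sample**
- SAP 3.8.1 (imputing a missing last dose date) and SAP 4.2.1 (exposure) exclude the 30-Day Follow-Up by name. The HIV-1 RNA window rules do not.
- CD4 has the same open Week 32 window and also takes the latest record, but its on-HIV-treatment limit removes the follow-up sample. HIV-1 RNA under M = F and M = E has no such limit.

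**Step 4: size at Week 32**

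Let *b* be subjects in an arm who are < 50 on drug and ≥ 50 at follow-up, and *c* those not counted as < 50 on drug but < 50 at follow-up. Under M = F the arm's rate shifts by (*c* − *b*)/60.
- One net subject: 1/60 = 1.7 points.
- The documents give neither *b* nor *c*. For illustration only, 1 to 6 net subjects give 1.7 to 10.0 points.
- Nearly all Week 32 values may be replaced, but the rate moves only where the two samples disagree.

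**Step 5: earlier visits**

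The Week 24 and earlier windows are closed and are affected only for subjects who stopped HIV study drug. Each one suppressed on another regimen adds 1.7 points to an arm of 60. The protocol's background suggests that virologic failure after a switch is rare: 10 of 959 in the E/C/F/TAF switch study, or 60 × 10/959 = 0.6 subjects per arm. Stops for other reasons would add to this, but no rate is given.

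**The case against.** **Importance.** A reader might infer that this undermines the secondary objective of maintaining HIV suppression. It does not. That objective is fixed at 24 weeks, and its endpoint is the snapshot, which is limited to on-HIV-treatment data in a closed window. SAP 6.3.2.6 is tertiary, and its differences carry an interval but no stated test. This objection stands and limits the weight of the point.

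**Replacement therapy.** A reader might also infer that nearly every completer's Week 32 result reflects a replacement regimen credited to the randomised one. The documents show only that completers are off study supply. Protocol 6.12 leaves later care to the treating physician, and both regimens are commercially available (Protocol 5.2.2.1 and 5.2.2.2), so a completer may be on the same tablet. A change of regimen is documented only for Part 2 discontinuers. This objection also stands.

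**Deliberate choice.** SAP 3.1.2 expressly includes data after the last dose, and M = F and M = E can be read as a treatment-policy complement to the on-treatment snapshot. For discontinuers this is a fair reading, although the SAP does not state it. It does not explain why a completer's on-drug Week 32 sample should give way to a later one when the SAP itself equates Week 32 with Post-HCV Treatment Week 12.

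**Part 1 discontinuers.** They leave after the early discontinuation visit and the 30-Day Follow-Up, so at most about one window holds an off-drug value. Their later windows are missing and count as failures under M = F.

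**Text gap.** The body of SAP 6.3.1 is not legible in the copy read, so a restriction there cannot be ruled out. None appears in 6.3.2.6, where the method is given.

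**Conclusion.** The Week 32 defect holds as written. An open window, the latest-record rule and the all-data default together select a sample 24 to 36 days after study drug for every completer who attends the follow-up. The direction of the error is unknown, and its size is 1.7 points per net discordant subject in an arm of 60. This assumes planned arm sizes, visits within their windows, and no restriction in SAP 6.3.1.

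For subjects who stop HIV study drug early, including later data is an estimand choice that needs a label; it is not an error. No primary or secondary result changes. The point merits correction because it alters a reported result and its between-arm interval and is easily put right.

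**What to change.** **Week 32.** Add one sentence to SAP 6.3.2.6, and mirror it in Appendix 4 item 11: either the 30-Day Follow-Up is excluded from the Week 32 HIV-1 RNA window, or that window uses only on-HIV-treatment data (last dose + 1 day). Either way a completer's Week 32 value becomes the Post-HCV Treatment Week 12 sample. A fixed upper study day would separate the visits less cleanly: Protocol 6.9.1 allows LDV/SOF to start up to 4 weeks late after an unconfirmed Week 6 rebound, which puts that subject's nominal Post-HCV Treatment Week 12 visit at 224 + 28 = Day 252, inside other subjects' follow-up range.

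**Discontinuers.** Either apply to all visits the on-HIV-treatment limit already used for the snapshot and CD4, or state that M = F and M = E are treatment-policy analyses that include data after a change of regimen.

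**Cost.** No new data and no design change. With the on-treatment limit, M = F rates may fall slightly, because suppressed discontinuers become failures. M = E rates may rise, because post-discontinuation values, including failures, are dropped. Early discontinuation visits may take place up to 72 hours after stopping, so some of those samples would fall outside last dose + 1 day and be lost. Excluding the 30-Day Follow-Up by name avoids these effects for subjects who complete treatment.
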